Upon study enrollment, participants will be randomized to receive either placebo or propranolol for a period of 12 weeks during the study. Drug randomization will be counterbalanced to ensure that half of the participants will receive placebo and the other half will receive propranolol. Randomization will also be double-blinded so that neither participants nor the researchers performing analysis will be aware of the identity of the drug being administered. As participants will be receiving varying levels of intensity of EIBI (number of hours per week), randomization will also be stratified according to different levels of intensity to ensure approximately equal distribution of EIBI intensity between the two drug groups.

The following are brief descriptions of the drugs to be administered:

Propranolol [pro-pran'-o-lol] blocks the brain's and body's use of norepinephrine both centrally and peripherally and also is commonly used to decrease high blood pressure.

Placebo [pla-see'-bo] is a physiologically inactive suspension that looks like other drugs.

Drug administration: Propranolol will be administered in the form of a liquid dose via oral syringe by the participants' parent/caregiver an hour before each EIBI session. Drug administration will begin after the first (baseline) study visit. To minimize risk, the bodyweight adjusted minimum dose of propranolol used safely for test anxiety in healthy adults (10mg) will be used (see table below):

Bodyweight (kg)	Dose (mg)
> 30	4
22.5 - 30	3
15 - 22.5	2
< 15	N/A

This more cautious dosing strategy will be utilized for safety purposes, as children may be less able to report potential side effects. Participants weighing less than 15kg will be excluded for safety reasons.

Heart rate and blood pressure monitoring: Participants with a heart rate of less than 60 or a systolic blood pressure of less than 75 at the outset of the study will be excluded. Heart rate and blood pressure will also be measured via wrist cuff at each study visit. If on any measurement the heart rate or systolic blood pressure is abnormal, the PI will be immediately notified. At this point, the PI may withdraw the participant from the study for safety reasons.

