Participation in this study will last 12 weeks and will involve 3 visits to the Thompson Center for Autism & Neurodevelopmental Disorders lasting approximately an hour and a half each. If a private room is not available at the Thompson Center when a participant's visit needs to be scheduled, the visit will take place at the Center for Translational Neuroscience (M741) in the Medical Sciences Building instead.

c. Blinding, including justification for blinding or not blinding the trial, if applicable.

This study will be double-blinded for the purposes of removing any bias that could be introduced if either the researchers or the study participants are aware of which drug they are taking at a given time. Blinding of the drugs will be conducted by the University Hospital's Investigational Pharmacy. In the case of emergency, the PI and research staff running study sessions will have access to unblinding information in the form of a sealed envelope.

d. Justification of why participants will not receive routine care or will have current therapy stopped.

Routine care for this population will not be affected by this study. Participants will be able to continue routine care, including behavioral therapy or other medications. Potential participants taking medications that are exclusionary for this study will not be enrolled.

e. Justification for inclusion of a placebo or non-treatment group.

A placebo arm of this study will allow for statistical comparisons between behavioral performance for participants who are taking placebo versus propranolol. The parallel design of the trial will involve half of the participants receiving propranolol and the other half receiving placebo. Drug randomization will be counterbalanced.

f. Definition of treatment failure or participant removal criteria.

As this is a pilot trial exploring the effects of propranolol on social and language abilities, there are no behavioral endpoints that we would consider treatment failure. However, for the safety of the participants, if at any measurement taken, a participant's heart rate or blood pressure is abnormal or if the participant is experiencing an adverse reaction to the drug the PI will be immediately notified. At that point, if the PI determines it is necessary, the participant will be instructed to discontinue taking the drug and will be removed from the study.

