g. Description of what happens to participants receiving therapy when study ends or if a participant's participation in the study ends prematurely.

When the study ends or if a participant's participation ends prematurely, the participant will no longer take propranolol or placebo. Participants will continue with their routine care as they would have done throughout the study.

5. **Inclusion/Exclusion Criteria**

Inclusion criteria:

For participants with autism: Individuals with ASD aged 3-8. ASD is defined in this study by the DSM-V criteria plus Autism Diagnostic Observation Schedule (ADOS) criteria for Autism. Participants must also be enrolled in an EIBI program at the Thompson Center or another institution in Missouri for the duration of the study.

For parent/caregiver of participant with autism: Minimum age of 18, no maximum age.

Exclusion criteria:

For participants with autism: Non-autism learning disability (e.g. dyslexia), major psychiatric diagnosis (e.g. major depression, schizophrenia, bipolar disorder), other neurological diagnosis, major head trauma, any of the following exclusionary criteria related to propranolol (diabetes, reactive airway/pulmonary disease, thyroid disease, bradyarrhythmias, unexplained syncope, narrow angle glaucoma, known hypersensitivity/adverse reaction to beta-blockers, potentially interacting drugs, underweight < 15 kg), any of the following exclusionary criteria related to the use of electrocardiogram (history of rash from adhesives), or any of the following exclusionary criteria related to the pupillary response measurement (uncorrectable visual acuity impairment). Participants with a heart rate of less than 60 or a systolic blood pressure of less than 75 at the outset of the study will be excluded.

For parent/caregiver of participant with autism: No exclusionary criteria.

6. **Drugs/ Substances/ Devices**

a. The rationale for choosing the drug and dose or for choosing the device to be used.

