To determine the appropriate sample size for this study, we conducted a power analysis based on effect size estimates on our previous study examining the effects of propranolol on social functioning in ASD. The power analysis indicated that a sample size of 20 would achieve a proposed power of 0.80 at the significance level of $\alpha = .05$. Behavioral assessments will be compared across study time points and between drugs (propranolol and placebo) using repeated measures multivariate analyses of variance (MANOVAs). We will use simple linear regressions to determine whether variability in baseline autonomic nervous system functioning or anxiety serve as markers to predict treatment response. Interim data analysis will only be conducted for the purposes of presenting preliminary data at academic conferences. The investigational pharmacy will assist in unblinding collected data for these preliminary analyses, keeping investigators blinded throughout the study.

- d. Early stopping rules.

As this is a pilot trial exploring the effects of propranolol on social and language abilities, there are no behavioral endpoints that we could consider treatment success or failure prior to the completion of the study, thus we would not stop the study based on early evidence of treatment efficacy or futility. If safety becomes a concern due to side effects associated with propranolol, the PI (in consultation with the HS IRB) may decide

to stop the study early. However, this is not expected to occur given the minimal side effects known to be associated with this drug at these doses.

8. Risks

- a. Medical risks, listing all procedures, their major and minor risks and expected frequency.

The medical risks participants may encounter are those associated with taking the drugs used in this study. Below are the descriptions and side effects associated with each drug:

Propranolol [pro-pran'-o-lol] is commonly used to decrease high blood pressure. This drug can cause problems for persons with depression, diabetes, thyroid disease, very slow heart rates, very low blood pressure, fluid in the lungs from heart failure, and asthma. The side effects related to this drug are given below. These symptoms are most present within 5 hours of the drug administration. None of these symptoms will be present once the single dose is washed out of the system, which can take up to 24 hours.

- Very Likely: Decreased Blood Pressure and/or Slow Heart Rate

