Given the chance of unforeseen side effects associated with the drug in participants who met criteria for participating in the study, monitoring of heart rate and blood pressure will occur at each of three study visits. If on any measurement the heart rate or systolic blood pressure is abnormal, the PI will be immediately notified. At this point, the PI may withdraw the participant from the study for safety reasons. Participants with a heart rate of less than 60 or a systolic blood pressure of less than 75 at the outset of the study will be excluded.

At each study visit taking place at the Thompson Center for Autism & Neurodevelopmental Disorders or the Center for Translational Neuroscience, a member of the study staff will first confirm with the participant and his/her parent/caregiver that no changes in the participant's physical condition have occurred since he/she met with the PI in person. A medical and pharmaceutical history will also be obtained to ensure the participant's condition has not changed in a way that would increase the risk of taking propranolol. Any new symptoms or diagnoses will be reported to the PI, who will follow-up with the participant and parent/caregiver if necessary.

Participants with previously documented history of rash from adhesives will be excluded from the study. This will minimize the risks associated with the ANS measurements taken during the study sessions.

To minimize the risk of boredom, participants will be given the opportunity to take breaks and ask any questions they have.

To minimize the risk of probing for personal and/or sensitive information, testing will take place in a private room at the Thompson Center. If participants have difficulty with disclosure of information on some surveys, they will be reminded that their answers will be kept securely and are confidential.

To minimize the risk of loss of privacy, the data will be coded, password-protected, and stored separately from the consent and screening forms in a locked filing cabinet. However, in the unfortunate event that a loss of privacy occurs, it is possible that information related to a participant's autism diagnosis and performance on the tests being administered will be obtained.

c. Plan for reporting unanticipated problems or study deviations.

Any unanticipated problems or study deviations will be immediately reported to the PI and HS IRB via an Event Report for further investigation.

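### Removal for safety ends outcome assessment as well as study drug, so removals before week 12 that differ by arm and relate to outcome could leave a comparison of selected children

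*Combined protocol and SAP*

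**What the plan says.** Section 4f names the triggers: an abnormal heart rate or blood pressure reading, or an adverse reaction. It then says that "if the PI determines it is necessary, the participant will be instructed to discontinue taking the drug and will be removed from the study". Section 4a, on heart rate and blood pressure monitoring, says: "At this point, the PI may withdraw the participant from the study for safety reasons". Section 8b repeats that "the PI may withdraw the participant from the study for safety reasons". All three leave the decision to the PI, and none gives a numerical threshold after baseline.

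Section 4g covers premature ending. It says that "the participant will no longer take propranolol or placebo" and that routine care goes on; it mentions no later assessment. Section 4a places outcome visits at weeks 0, 6 and 12 only.

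For the analysis, section 7c says: "Behavioral assessments will be compared across study time points and between drugs", by repeated-measures MANOVA. It names no analysis set and no rule for children with a missing visit.

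**The concern.** Stopping a drug and stopping measurement are separate decisions, and the plan joins them. A child removed after the week-1 safety call would contribute baseline only. A child removed at week 6 would lose week 12. Removal at the week-12 visit need lose nothing.

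The triggers could differ by arm. Section 8a puts lowered blood pressure or slow heart rate in its most likely category for propranolol and says that placebo carries no risk. They could also be related to outcome: section 2 expects autonomic activity to predict response to propranolol, and two of the triggers are cardiovascular. This does not establish a correlation, but zero correlation cannot be taken for granted.

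If both conditions hold, the children compared at week 12 are no longer the groups that were randomised. Outcomes never collected cannot be recovered later, and any analysis must then rely on assumptions the data cannot test.

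**Working it through.** **Figures in the plan.** The plan states no expected removal rate, so there is no figure of its own to reproduce. Section 4a recruits 30 children, half to each drug, so 15 per arm. Section 7c's power analysis gives 20. The extra 10 are not described as a dropout allowance (20/(1 − 1/3) = 30 would imply one third lost), and larger enrolment would not remove selection bias.

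**Assumptions.** No true drug effect; outcome SD of 1; equal correlation r between visits; k children with the most extreme removal tendency are lost from one arm and none from the other. Removal tendency has correlation rho with the week-6 and week-12 scores and b with baseline.

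**Step 1: mean shift m in removal tendency among those kept.** From normal order statistics for 15 children:
- k = 1: m = 1.736/14 = 0.124
- k = 3: m = 3.93/12 = 0.327

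**Step 2: complete-case bias.** Raw week 12: rho × m. Change from baseline: (rho − b) × m.

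| Removed | rho | Raw week 12 | Change, b = 0 | Change, b = rho |
|---|---|---|---|---|
| 1 of 15 | 0.3 | 0.04 | 0.04 | 0 |
| 1 of 15 | 0.5 | 0.06 | 0.06 | 0 |
| 3 of 15 | 0.3 | 0.10 | 0.10 | 0 |
| 3 of 15 | 0.5 | 0.16 | 0.16 | 0 |

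With rho = 0 there is no bias.

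**Step 3: standard error.** Raw, 12 v 15: sqrt(1/12 + 1/15) = 0.387. The largest raw bias is 0.164/0.387 = 0.42 of a standard error. For change, the variance is multiplied by 2(1 − r): the standard error is 0.387 at r = 0.5 and sqrt(0.6 × 0.15) = 0.300 at r = 0.7. The largest change bias is therefore 0.42 or 0.55 of a standard error.

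**Step 4: does a mixed model cure it?** If week 6 is observed and week 12 is lost, the remaining bias is [rho − (r/(1+r)) × (b + rho)] × m. With k = 3 and rho = 0.5:
- r = 0.5, b = 0: (0.5 − 0.333 × 0.5) × 0.327 = 0.11
- r = 0.7, b = 0.5: (0.5 − 0.412 × 1.0) × 0.327 = 0.03

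Setting this equal to (rho − b) × m gives b = r × rho. Where b lies between r × rho and rho, the mixed model is more biased for change than complete cases.

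**Step 5: full follow-up.** With week-12 data on every randomised child, simulated bias was 0.00 in the settings run. Those runs set the true effect to zero, so this concerns the effect of assigned treatment only.

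**Step 6: dilution.** If 3 of 15 stop and keep no drug effect, the average effect in the arm is 12/15 = 80% of the on-drug effect, a 20% reduction.

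**The case against.** The strongest reply is that few children may be removed. Section 7d expects minimal side effects at these doses. Section 5 excludes "Participants with a heart rate of less than 60 or a systolic blood pressure of less than 75 at the outset of the study". Section 8b says that "monitoring of heart rate and blood pressure will occur at each of three study visits"; the first of these precedes any drug and none is tied to a dose, although section 8a says effects are mostly seen within 5 hours. The side-effect list is itself written around a single dose. Removal is discretionary and decided within a double-blind design. Blinding limits removal driven by knowledge of the arm, though not physiological differences. All of this stands: removals may be few or none.

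Section 7c compares across time as well as between drugs, so the change contrast matters more than raw week-12 scores, and there the bias can vanish. This also stands, and is why the range is 0 to 0.16 SD.

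Follow-up off drug has a price. Section 7c gives no effect size, but a sample of 20 at 80% power and two-sided 0.05 implies a standardised effect of 0.66 if paired or 1.32 with 10 per arm. A 20% dilution would then be 0.13 or 0.26 SD, comparable with or larger than the bias avoided. The SRS, one of two primary measures, is parent-reported, and a parent told to stop drug may guess the arm. These are real costs. Dilution, however, reflects a different treatment effect, while selection is an uncontrolled error; an on-drug sensitivity analysis can show the contrast.

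The point about incomplete cases is also limited. Dropping a child with a missing visit is the usual default for this method, not a rule the plan states, and section 4g's silence on outcome visits is weak evidence by itself.

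**Conclusion.** The point holds conditionally. The plan contains a rule that ends measurement together with treatment, and describes no outcome visit afterwards. If removals before week 12 differ by arm and relate to outcome, the comparison may rest on selected children. In the illustration (3 of 15 removed from one arm, correlation 0.3 or 0.5) the bias is 0.10 or 0.16 SD in raw week-12 scores and 0 to 0.16 SD in change, against a raw standard error of about 0.39 SD. With 1 of 15 removed the raw figures are 0.04 or 0.06 SD. Every removal rate and correlation here is assumed.

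A reader might infer that the trial will be biased towards propranolol because lowered blood pressure or heart rate is listed as very common. The documents do not support that. They give no removal rate, and the direction is open: it favours propranolol if children who tolerate it poorly do worse, and goes against it if strong responders to beta-blockade are the ones removed. Nor does a mixed model alone solve the problem, and full follow-up does not remove bias for an on-drug effect.

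Severity is low to moderate in a pilot. Confidence is medium.

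**What to change.** Leave unchanged the PI's existing authority to stop drug or to end study procedures for safety.

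- **Sections 4a, 4f, 4g and 8b:** add that a child who stops study drug is not, for that reason alone, removed from outcome assessment, and that the week-6 and week-12 assessments are sought where consent continues and the PI has no safety objection to them.
- **Section 7c:** analyse all randomised children in their assigned arm, including outcomes collected after drug is stopped, with a method that keeps available visits. Do not claim that the method removes selection bias.
- **Reporting:** give removals by arm, timing and reason, and add an on-drug sensitivity analysis. Interpret SRS scores after stopping with possible arm-guessing in mind.

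The cost is mainly protocol and analysis wording. The week-6 and week-12 visits, and payment for each completed visit, are already planned. Whether consent wording would also change cannot be judged, because the consent pages are not available. The statistical price is dilution of an on-drug effect, up to the 20% shown above if 3 of 15 stop and keep no effect.

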- a. Study design, including the sequence and timing of study procedures (distinguish research procedures from those that are part of routine care).

The proposed study is a 12-week, parallel design, placebo-controlled pilot trial. For the purposes of this study, we will recruit 30 participants with ASD aged 3-8 who are currently enrolled in an EIBI program. ASD is defined in this study by the DSM-V criteria plus Autism Diagnostic Observation Schedule (ADOS) criteria for Autism. Participants will be screened for this formation as well as inclusion/exclusion criteria to determine their eligibility to participate in this study over the phone prior to obtaining written consent. A waiver of documentation of consent is requested for these screening purposes only. Written consent will be obtained prior to any other study-related procedures. The ADOS may be administered during the initial study visit if a prospective participant does not have ADOS scores from a previous assessment. Additionally, an intellectual assessment (IQ test), the Differential Ability Scales (DAS), may be administered at this time if previous scores do not exist.

Prior to participation in the study, informed consent will be obtained from both parents/legal guardians of the participant, and assent will be obtained from the participant. In addition, the parents and participants will be informed that they can terminate the procedure and exit the study at any time.

We will recruit participants during their participation in the EIBI program at the Thompson Center or other institutions in Missouri. The EIBI team provides one-on-one instruction for individuals with ASD, as they work toward treatment goals of learning new skills and minimizing challenging behavior. EIBI staff will be also be blinded to drug conditions. Given the highly individualized nature of EIBI, each participant's therapy will differ in frequency of sessions per week and length, as well as defined behavioral targets and the methods used to reach them. This variability will be accounted for via a stratified randomization approach (see below) as well as statistically during analyses after study completion.

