During the study, participants will undergo ANS activity and behavioral assessments (discussed below) at three separate study visits at the following time points: (1) prior to drug administration, for establishment of a baseline (week 0); (2) at approximately week 6; and (3) at the end of week 12. Each study visit is expected to last approximately an hour and half.

ANS Measurements: At each study visit, ANS measurements will be performed to assess autonomic activity. Heart rate variability (HRV), measured via electrocardiogram, will be used to assess sympathetic and parasympathetic nervous system activity. Electrodes will be placed on the chest region in the typical manner, and signal from the electrodes will be amplified by an ECG 100C module connected to a BIOPAC MP150 data acquisition system. Measurements will be recorded for a period of 8 minutes, allowing for 3 minutes of acclimation to the equipment.

We will also evaluate ANS activity via the pupillary light reflex (PLR), a simple functional neurological test measuring pupil constriction and recovery in response to stimulation via a short light flash. During the test, the participant will sit comfortably in a

chair or will be seated on a parent's lap about 1 m from the PLR system. A red-filtered movie will be shown on a projector screen behind the PLR system to attract the participant's attention. During the test, participants' PLR will be assessed in both light- and dark-adapted conditions. A total of 10 trials, each lasting 2.5 sec followed by a 25-30 sec interval, will be performed for each stimulation condition.

Behavioral Assessments: Behavioral tasks and questionnaires will also be performed at each study session. The following assessments will be completed by the participant with ASD:

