(2) Interval Medical History Questionnaire: Participants' parents/caregivers will complete a questionnaire about any side effects their child has experienced since the previous study visit, any new medical or psychiatric diagnoses, and any concomitant medications they are taking or have added since the last study visit, and whether they have visited a doctor's office or hospital since their last study visit. This questionnaire is for the purpose of maintaining the safety of participants, as the study staff and PI

will need to ensure that each participant is not experiencing any adverse events throughout the study.

(3) Demographic questionnaire: A questionnaire ascertaining a participant's personal and family demographic information, such as race/ethnicity, handedness, and socioeconomic status, will be completed by the parent/caregiver at the initial study visit only.

(4) Social Responsiveness Scale, second edition (SRS): This 65-item, parent-report measure asks questions about a participants' social awareness, social information processing, capacity for reciprocal social responses, social anxiety or avoidance, and characteristic autistic preoccupations or traits. Depending on the child's age, the preschool or school-age version of the SRS will be administered.

(5) Clinical Global Impression of Change (CGIC) and Clinical Global Impression of Severity (CGIS) scales: To assess overall changes in the participant's ASD-related clinical symptoms, the CGIC and CGIS will be administered. The CGIC consists of a 7-point subjective scale assessing change from baseline. On this scale, scores of 1, 2, and 3 represent marked, moderate, and mild improvement, respectively. A score of 4 represents no change. Scores of 5, 6, and 7 represent mild, moderate, and marked worsening, respectively. CGIC scores from both the parent/caregiver and a blinded clinician will be utilized. The CGIS is a similar 7-point subjective scale for severity.

(6) Autism Impact Measure (AIM): The AIM will be administered to assess the frequency and impact of a participant's ASD-related symptoms. A parent/caregiver is asked a series of 41 questions regarding the frequency and the impact, or interference resulting from, a series of autism-associated behaviors. Overall impact and frequency scores, as well as subscale scores, will be obtained from this measure.

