- Less Likely: Decreased Sex Drive or Impotence
- Rare: Abdominal Cramps, Diarrhea, Constipation, Fatigue, Depression, Vivid Dreaming and/or Tingling Sensations
- Rare but more Serious Side Effects: Insomnia, Nausea, Hypersensitivity/Allergy, Dizziness, Drowsiness or Lightheadedness, Very Slow or Uneven Heartbeats, Swelling of Ankles/Feet and/or Difficulty Breathing

Placebo [pla-see'-bo] is a physiologically inactive suspension that looks like other drugs. The placebo doses will not have any risk associated with their administration.

Participants may also encounter minor risks associated with the adhesives used to collect ANS data via electrocardiogram. Participants may develop a small rash where the sensors attach to their chest. If this occurs, the rash normally subsides shortly after the study visit. Participants and their parents/caregivers will be asked to notify a member of the study staff or the PI if the rash persists.

There are also psychological risks of boredom and probing for personal and/or sensitive information in the tasks and questionnaires the participants will complete as part of this study.

There is the potential risk of a loss of privacy, in which information related to participants' autism diagnosis and their answers to the tasks and questionnaires being administered will be obtained.

- b. Steps taken to minimize the risks.

Strict adherence to the exclusionary criteria of this study will minimize the chance of enrolling participants who might be put at risk by taking propranolol. Before enrollment in the study, the PI (a licensed physician) will meet in person with prospective

participants and their parents/caregivers to evaluate their ability to safely take part in this study. Upon enrollment in the study, participants' parent/caregiver will be given a business card containing contact information for lead study staff and the PI in case of questions and/or emergency. Additionally, one week after the initiation of drug administration (at approximately week 1), a member of the study staff will call the participants' parents/caregiver to inquire about any possible side effects associated with the drug (listed above). Any reports of adverse response to the drug will be communicated to the study PI.

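### No side-effect form or contact is specified when a child leaves between visits, so side effects behind voluntary early exits may go unrecorded

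*Combined protocol and SAP*

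**What the plan says.** **Form.** The Interval Medical History Questionnaire (section 4a, parent/caregiver assessments, item 2) is the side-effect instrument. Parents "will complete a questionnaire about any side effects their child has experienced since the previous study visit". Section 4a also says that "Behavioral tasks and questionnaires will also be performed at each study session".

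**Visits.** The baseline visit comes before the first dose. The later visits are listed as "2) at approximately week 6; and (3) at the end of week 12". Section 4b adds: "Participation in this study will last 12 weeks and will involve 3 visits".

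**Exit.** Under section 4a, "the parents and participants will be informed that they can terminate the procedure and exit the study at any time". Section 4f lets the PI remove a child for an abnormal heart rate or blood pressure or for an adverse reaction, after being notified. Section 4g, the passage on premature ending, states: "When the study ends or if a participant's participation ends prematurely, the participant will no longer take propranolol or placebo". It adds that routine care goes on, and nothing about a last form, visit or call.

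**Other routes.**
- Section 8b schedules one call at about week 1, when "a member of the study staff will call the participants' parents/caregiver to inquire about any possible side effects associated with the drug". It also gives families a card with contact details and sends reports of adverse response to the PI.
- Section 6b encourages parents to discuss side effects with the PI or their own doctor.
- Section 8c requires Event Reports for unanticipated problems and deviations.
- The exit survey in section 4a is for families who complete the study. It asks about their experience and their suggestions.

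**The concern.** Followed exactly as written, the plan collects a side-effect form only from children who reach the next visit. Families who stop because a child is drowsy or sleeping badly are more likely than others to miss it. The missing intervals are then not a random sample of follow-up, and they would tend to come from children who tolerated treatment less well.

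The record matters for this trial's own purposes. Section 4a gives the questionnaire a safety role. It also acknowledges that children may be less able to report side effects. Section 7d leaves any early stop for safety to the PI's judgement of side effects, in consultation with the IRB. The abstract describes the trial as the first study of the drug's effects in children with autism, so its side-effect record is likely to be consulted when later studies are planned.

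**Working it through.** The documents give no dropout rate, adverse-event rate or safety sample size, so there is no figure of the plan's own to reproduce. The check has three parts: read the sections together, then illustrate the possible size under stated assumptions, and then vary those assumptions.

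**1. Which intervals lack a form**

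| Time of exit | Forms after dosing starts | Other scheduled side-effect contact | Interval with no form |
|---|---|---|---|
| Before about week 1 | none | none certain | start to exit |
| After the week-1 call, before week 6 | none | week-1 call | up to about 6 − 1 = 5 weeks after the call |
| After week 6, before week 12 | week 6 | week-1 call | up to about 12 − 6 = 6 weeks |
| Completes | weeks 6 and 12 | week-1 call | none |

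**2. Whether the other routes close the gap**
- *PI notification (4f).* A child removed for a reaction is known to the PI before removal. What is missing is a standard record, not knowledge of the event.
- *Week-1 call (8b).* It is scheduled for all families but happens once, at the start of the first interval.
- *Contact card and discussion with the PI (8b, 6b).* These depend on the family choosing to report.
- *Event Reports (8c).* They cover unanticipated problems and deviations. Drowsiness, insomnia, nausea and fatigue are on the list of known effects in section 8a, so an exit over one of them need not trigger a report.
- *Exit survey (4a).* It is for completers and is not a side-effect form.

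What remains is mainly voluntary exit after week 1, for an expected effect, with no reason volunteered.

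**3. Worst-case illustration**

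Inputs from the documents: 30 children (4a), half to each arm (4a), so 30/2 = 15 per arm.

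Assumptions: one specific side effect; one affected propranolol child, who leaves before week 6; no other affected child; no capture by any other route.

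The one-sided 95% Clopper-Pearson upper limit U for x events in n children solves P(X ≤ x | n, U) = 0.05.
- Recorded, 0/14: (1 − U)^14 = 0.05, so U = 1 − 0.05^(1/14) = 0.193.
- True, 1/15 (6.7%): (1 − U)^15 + 15U(1 − U)^14 = 0.05, so U = 0.279.

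**4. How far this depends on the assumptions**
- *Exit after week 6.* The child already has a week-6 form and stays in the denominator. The record is 0/15, with U = 1 − 0.05^(1/15) = 0.181, against the same 0.279.
- *Other children also affected.* Take 6/15 truly affected (40%; U = 0.640) and lose one before week 6. The forms show 5/14 (36%; U = 0.610). The contrast is much smaller.
- *Capture by other routes.* Suppose the true rate is 40% and 25% of affected children leave between visits. If a share c of those leavers is captured elsewhere, the recorded rate per 15 children is 0.40 × [1 − 0.25(1 − c)]. This gives 30% at c = 0, 35% at c = 0.5, and 40% (no loss) at c = 1.
- *Number of leavers.* With an assumed dropout rate q between visits, the expected number is 30q and the chance of at least one is 1 − (1 − q)^30. For q = 5%, 10% and 20% this gives 1.5, 3 and 6 children, and probabilities of 0.785, 0.958 and 0.999.

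**The case against.** The strongest reply is that having no form is not the same as having no record. A reaction leading to PI removal is known to the PI. Every family is due a call at about week 1 and has contact details, and reported reactions go to the PI. Children who have side effects and stay are recorded at the next visit. This is also a brief pilot protocol, and no section contradicts another. All of that stands, and it narrows the point mainly to families who withdraw on their own after week 1 without giving a reason. It does not remove the point, because none of these routes asks a departing family what happened since the last form.

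The 19% against 28% contrast is also open to challenge. It assumes nobody else is affected, and section 8a rates lowered blood pressure or slow heart rate as very likely. No side-effect rate or interval is planned in section 7. The figures are therefore an illustration and not a forecast.

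Three stronger readings are tempting, and the documents do not support them.
- *That the trial under-reports harm.* This would need leavers, exits caused by side effects, and failure of the other routes. No figure is given for any of these.
- *That this is the first use of propranolol at this age.* The abstract claims novelty only for children with autism, and section 6b cites established paediatric use.
- *That the lack of contact after the last dose is a serious gap in itself.* Section 8a says "None of these symptoms will be present once the single dose is washed out of the system, which can take up to 24 hours". That sentence concerns a single dose and the trial gives repeated doses, but it still leaves this part with little weight.

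**Conclusion.** The gap is real and limited. No form or contact is specified at early exit, so side effects in children who leave between visits may be incompletely recorded, and the loss is likely to be related to tolerability. That last step is a judgement about why families leave. The documents do not report it.

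Neither the size nor the direction of any difference between arms can be computed. The worst case, on the four assumptions stated with it, is 0/14 (upper limit 19%) recorded in place of 1/15 (28%). The loss falls to nothing if the other routes capture every such case. The point concerns completeness of the safety record. It does not show that any harm will be missed.

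**What to change.** In section 4g and in the description of the Interval Medical History Questionnaire, state that at any early exit, whether the family or the PI initiates it, study staff complete the existing questionnaire by phone with the parent or caregiver, if the parent agrees. State that it covers the time since the last form (or since dosing began, if there is none) and the reason for leaving. State that these forms are counted with the week-6 and week-12 forms in any side-effect summary, and that the number of leavers without a form is reported by arm.

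The cost is a wording amendment and one short call per leaver, using a form already in use and staff who already make the week-1 call. Some families will decline, so the gap will shrink but may not close. No dose, stopping or removal rule changes.
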